- Presence of another painful condition of greater severity than the back pain condition which is being studied.
- History of traumatic brain injury.
- Clinically significant or unstable medical condition. Individuals with significant cardiovascular, hepatic or renal disease, uncontrolled hypertension, and chronic pulmonary disease (eg, asthma, COPD), will be excluded. With respect to cardiovascular and pulmonary status, a clinician will screen participants with a tool developed for detection of congestive heart failure, coronary artery disease, obstructive and/or restrictive lung disease (Appendix 28 Cardiopulmonary Screen). Hepatic and renal disease will be evaluated with liver and renal function laboratory tests. If warranted clinically, subjects will undergo further evaluation (urinalysis, electrocardiogram, and/or chest X-ray).
- A positive result on toxicity screening will exclude individuals from participation. A urine drug test that screens for 5 categories of drugs: marijuana ($\Delta 9$ -THC), cocaine, amphetamines/methamphetamines, opiates, benzodiazepines and phencyclidine (PCP) will be employed. A positive result for opioids and/or THC will not be exclusionary if the patient is receiving a prescription for an opioid and/or THC.
- Allergy to sesame oil, lactose, or gelatin
- Vascular disease, especially Raynauld's syndrome, systolic blood pressure > 170 mm, diastolic blood pressure > 100 mm
- Recent injuries to the upper extremity
- Cognitive impairment, such as Dementia or Alzheimer's Disease
- Substance Abuse History: individuals with current substance use disorders⁵⁵ as assessed using the Drug Abuse Screening Test (DAST-10) (a score greater than or equal to 3) and the Alcohol Use Disorders Identification Test (AUDIT) (a score greater than or equal to 8 or a score greater than or equal to 7 if over 65 years old) (Appendix 31).
- Pregnancy as ascertained by a mandatory commercial pregnancy test
- Women who are lactating

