15. RISK MANAGEMENT PROCEDURES AND ADEQUACY OF RESOURCES

At every study visit, stopping criteria will include:

Pulse: an irregular pulse or pulse rate > 110 beats per minute

Blood Pressure: systolic blood pressure > 180 mmHg or diastolic > 110 mmHg

Respirations: respiratory rate > 20 breaths per minute

Pulse: an irregular pulse or pulse rate greater than 110 beats per minute will result in cessation of participation and, if deemed advisable by a study clinician, transfer to the emergency department (across the street from our research center).

Blood Pressure: If the systolic blood pressure is ≥ 160 to < 180 mmHg or the diastolic is ≥ 100 to < 110 mmHg, a study clinician will conduct an evaluation to see if the participant has symptoms that would mandate discontinuation. Examples would include severe headache, confusion, chest pain, dyspnea, irregular heartbeat, and/or palpitations. Final determination regarding possible discontinuation will be made by a study investigator. If discontinued from the study, the participant will be asked to have their blood pressure evaluated by their primary care physician as soon as possible. If the systolic blood pressure is > 180 mmHg or the diastolic is > 110 mmHg, the participant will be discontinued from the study and either be transferred to the emergency department or be asked to visit their primary care physician as soon as possible. The end organ response to the blood pressure will guide the clinician's decision (e.g., the development of angina pectoris or hemiplegia will mandate transfer to the emergency department).

Respirations: shortness of breath will result in potential cessation of participation and possible transfer to the emergency department following evaluation by a study clinician, who will consult with the study investigator.

A locally developed self-report instrument, the Cannabis Solicited Adverse Events (Appendix 29) will be administered to assess distress from psychological effects of cannabis. This will be performed on a prn basis by the trained staff and routinely at the end of the acute

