- Preventing children and adolescents from gaining access to medicinal cannabis because of potential harm to their well-being. Subjects will be required to store cannabis in an area of their home that would prevent anyone else from discovering its location.
- Because some people cannot control their use of cannabis, we will not allow patients with recent substance abuse histories (less than 12 months) to participate.
- We will exclude patients if they are pregnant or refuse to exercise birth control if engaging in sexual activities that could result in pregnancy, have a heart disease or heart rhythm problem or have a history of serious mental illness (e.g., schizophrenia, mania, or a history of hallucinations or delusions)
- In order to avoid carcinogens, we will have subjects use a vaporizer rather than smoke joints or use a water pipe.

- We will instruct subjects not to drive a car or operate heavy machinery for 3-4 hours after use of medicinal cannabis, or longer if larger doses are used or the effects of impairment persist. They will use a designated driver for automobile transportation if they have to go out sooner than 3-4 hours after taking this medicine.
- As the response to cannabis varies widely, participants will titrate to effect and in essence use the minimum amount of medicinal cannabis needed to obtain relief from pain.
- A cannabis withdrawal syndrome will be under surveillance for two weeks; difficulty with getting to sleep and angry outbursts might require that they withdraw from the cannabis more slowly.

The UCSD Department of Psychiatry (Appendix 17) is committed to providing the resources and other supports (e.g., data management and information systems, statistical, and physical performance site) to ensure the timely implementation, conduct, and completion of this program.

Data and Safety Monitoring Board (DSMB)

A DSMB will be selected utilizing a group of experts that will advise the study investigators, with the primary responsibility to monitor human subject safety. The members will be comprised of at least 3 independent clinicians familiar with the conduct of clinical trials. The DSMB will consider study-specific data as well as relevant background information about the test agents and target population under study. The DSMB will review the protocol, including the safety monitoring plan, and identify any major concerns prior to implementation. During the trial the DSMB will review:

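### Protocol sections 10 and 15 give different exclusion lists, so the same person can be eligible under one and excluded under the other

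*Protocol*

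**What the plan says.** Protocol section 10 (Human Subjects) sets out labelled inclusion and exclusion criteria. On the points at issue:

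- **Heart:** only cardiovascular disease qualified as significant is excluded. It is screened with "a tool developed for detection of congestive heart failure, coronary artery disease, obstructive and/or restrictive lung disease", and an electrocardiogram is done only if clinically warranted.
- **Blood pressure:** one bullet excludes "systolic blood pressure > 170 mm, diastolic blood pressure > 100 mm". Another excludes uncontrolled hypertension without giving a figure.
- **Substance use:** it excludes "individuals with current substance use disorders", judged by DAST-10 and AUDIT scores.
- **Mental illness:** it names schizophrenia, bipolar depression with mania, the wider spectrum around these, and suicidality.
- **Reproduction:** it lists pregnancy and lactation.

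Protocol section 15 (Risk Management Procedures) adds eligibility statements among its risk-mitigation measures. Patients are excluded if they "have a heart disease or heart rhythm problem or have a history of serious mental illness", and the examples of serious mental illness include past hallucinations or delusions. Refusal of contraception also excludes. On substance use, "we will not allow patients with recent substance abuse histories (less than 12 months) to participate".

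Section 15 also gives vital-sign rules for every study visit. For pulse, "an irregular pulse or pulse rate greater than 110 beats per minute will result in cessation of participation". The blood pressure stopping criterion reads "Blood Pressure: systolic blood pressure > 180 mmHg or diastolic > 110 mmHg". Below it lies a band that triggers a clinician's evaluation for symptoms: "If the systolic blood pressure is ≥ 160 to < 180 mmHg or the diastolic is ≥ 100 to < 110 mmHg".

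**The concern.** Both sections state who is kept out, in operative language, and neither refers to the other on these points. Section 10 looks like the list from which an enrolment checklist would be built. Section 15 presents its exclusions as protection against known risks, and section 14 lists increased heart rate among the likely ones. If screening runs from section 10 alone, some of those protections may not be applied.

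The conflict also leaves it unclear whether enrolling such a person is a protocol deviation. Deviations are an item in both the open and closed monitoring reports (SAP 6.1 and 6.2), so the question will have to be answered during the trial.

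**Working it through.** The plan gives no figure to reproduce here. The check compares the two sections item by item, then compares the blood pressure ranges.

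**Exclusions**

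| Topic | Section 10 | Section 15 | Eligible under 10, excluded under 15 |
|---|---|---|---|
| Heart | Significant cardiovascular disease; screen described for heart failure, coronary and lung disease | Any heart disease or rhythm problem | Rhythm problem, or heart disease not judged significant |
| Psychotic symptoms | Bipolar/schizoaffective/schizophrenic spectrum | Also past hallucinations or delusions | Such a history outside that spectrum |
| Substance use | Current disorder by questionnaire score | History within 12 months | A problem in the past year that is no longer current |
| Contraception | No criterion | Refusal excludes | A person who refuses |

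Two rows need qualifying. On contraception, section 14 says that participants will have to use birth control, so the requirement exists in the protocol but is missing from the eligibility list. On substance use, the documents give no look-back period for DAST-10 or AUDIT, so the difference may be one of wording only.

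**Pulse.** Section 10 has no criterion for rate or regularity. Section 15 makes an irregular pulse, or a rate above 110, a stop. A person can satisfy every listed section 10 criterion and already meet that stop.

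**Blood pressure.** Let S be systolic and D diastolic pressure in whole mmHg. I read section 10 as excluding a person when either limit is exceeded.

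- Admitted by section 10: S ≤ 170 and D ≤ 100.
- Evaluation band in section 15: 160 ≤ S < 180, or 100 ≤ D < 110.
- Stop limits in section 15: S > 180, or D > 110.
- Admitted and in the evaluation band: 160 ≤ S ≤ 170, which is 170 − 160 + 1 = 11 whole values, or D = 100, a single value.
- Admitted and beyond a stop limit: none. The highest admitted values lie 180 − 170 = 10 mmHg and 110 − 100 = 10 mmHg below the stop limits.

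The same comparison shows that S = 180 and D = 110 exactly fall in neither section 15 band.

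**The case against.** The strongest reply is that the lists are cumulative. This is a single-site study, section 15 says plainly that these patients will be excluded, and a person may satisfy section 10 and still be barred by section 15. That reading is possible, but the protocol does not state it. It would also leave section 10's narrower terms (significant, current) with little purpose. The telephone screen and the cardiopulmonary screen are appendices outside these documents and might cover rhythm or past-year use; that cannot be checked. Clinician judgement on unstable medical conditions, and the psychiatric questionnaires at the baseline visit (the PSQ and the Mood Disorder Questionnaire), may catch some of the people concerned. These points narrow the gap without closing it.

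A reader might go further and infer that people with an irregular pulse will be randomised, exposed to study drug and then stopped, with loss of primary-outcome data. The documents do not support that as a finding. The stop rules apply at every study visit. Protocol section 9 (Microbiome Assays) places the first experimental visit's samples before treatment, and the cold-pressor test, given at all study visits, includes blood pressure and heart rate. Such a person may therefore be stopped before dosing. The text does not fix the moment of randomisation relative to that check.

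A reader might also take the blood pressure overlap as a contradiction in the stop rule. It is not: the band opens an evaluation for symptoms, and someone without symptoms may continue. Nor is distortion of the discontinuation summary shown, because SAP 2.3 records dates and reasons by arm.

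**Conclusion.** The conflict between the exclusion lists holds. Four items in section 15 (heart disease or rhythm problem, past hallucinations or delusions, substance abuse within 12 months, refusal of contraception) are absent from section 10 or stated more narrowly there. The substance-use item is the weakest of the four.

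The vital-sign point is secondary. Section 10 is silent on pulse, and its blood pressure limits overlap the evaluation band at 160 to 170 mmHg systolic and at exactly 100 mmHg diastolic, never the stop limits.

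The documents give no frequency for any of these conditions, so the number affected among the 120 participants cannot be computed. Any percentage would be a guess, and adding evaluations to stops and setting the total against the planned 16% dropout would mix different things. Missed exclusions are a possible consequence, on the assumption that section 10 serves as the working eligibility list; exposure followed by a later stop is possible but not shown. No effect on the primary comparison is claimed. The point merits correction because the rules concerned are operative and safety-motivated.

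**What to change.** Reconcile the section 10 criteria with the exclusions and vital-sign rules in section 15, so that one eligibility list governs enrolment, and have other sections refer to it. Include the contraception requirement in section 14 in that reconciliation. State how the entry criteria relate to the on-study pulse and blood pressure rules, including how a finding already present at entry is to be handled, and settle the two unassigned values of 180 and 110 mmHg. Which criteria and thresholds apply is for the investigators to decide.

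The cost is amendment wording, a revised eligibility checklist and possibly a few more screen failures.

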4. ESTIMATED DURATION OF THE STUDY

We estimate that the study will take 4 years.

5. LAY LANGUAGE SUMMARY OR SYNOPSIS (no more than one paragraph)

This study will involve treating low back pain associated with nerve injury with two types of medicinal cannabis for eight weeks. Research subjects will consume either oral Δ9-THC (dronabinol), vaporized 4.0% Δ9-THC/6.5% CBD (estimated percentages), or placebo. An analysis will then be performed to assess the risk-benefit ratio of dronabinol and vaporized 4.0% Δ9-THC/6.5%. In addition, subjects will undergo driving simulation to determine how long it takes for them to recover from these medications.

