Both of the above studies were 6-hour human laboratory experiments. The present study is designed to evaluate whether or not the medium dose of cannabis (3.5%) can maintain an analgesic response over an eight-week period. In addition, a direct comparison of this vaporized preparation will be made with dronabinol and placebo. The medium dose of cannabis (3.5%) has been selected as it was utilized in a human experimental laboratory experiment that compared inhaled Δ9-THC and dronabinol.⁶ Using the cold-pressor test, participants immersed their hand in cold water (4 degrees C), and the time to report pain (pain sensitivity) and withdraw the hand from the water (pain tolerance) was recorded. Compared with placebo, marijuana and dronabinol decreased pain sensitivity, increased pain tolerance, and decreased subjective ratings of pain intensity. The magnitude of peak change in pain sensitivity and tolerance did not differ between marijuana and dronabinol, although dronabinol produced analgesia that was of a longer duration. Marijuana and dronabinol also increased abuse-related subjective ratings relative to placebo; these ratings were greater with marijuana. These data indicate that under controlled conditions, marijuana and dronabinol decreased pain, with dronabinol producing longer-lasting decreases in pain sensitivity and lower ratings of abuse-related subjective effects than marijuana.

A direct comparison of cannabis and dronabinol has not been performed in a clinical population. The present study will fill this void by performing a randomized, double-blind placebo controlled 8-week trial comparing the effectiveness of oral versus vaporized cannabis in patients with chronic low back pain. In addition to studying efficacy, we will also perform a driving simulation study to determine the real-world impact of cannabinoid treatments.

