By conducting repeat assessments for four hours following the first vaporization, we will be able to determine at what point participants no longer exhibit acute effects for each of the study medications. Participants will then complete a second vaporization and ingestion of oral medication before hour 6. We will then assess them for three hours in order to determine whether the acute effects are similar to those seen after the first vaporization, or perhaps greater (due to cumulative/residual effects). To minimize the novelty of the driving simulations, participants will complete a pretest training session to re-familiarize themselves with the hardware and the tasks that they are to encounter during the simulations. Four separate tasks will be embedded within the simulation.

Table 3 Assessments of Acute Effects One Day following 2 and 8 Weeks of Cannabis Treatment

Hour	1		2	3	4	5		6	7	8
		Vaporization/Oral Medication					Vaporization/Oral Medication			
Vital Signs	X		X	X	X	X		X	X	X
Numerical Pain Intensity Score	X		X	X	X	X		X	X	X
Cold Pressor Test	X		X					X		
Pain Relief			X	X	X	X		X	X	X
Psychoactive Effects			X	X	X	X		X	X	X
Driving Simulation	X		X	X		X		X	X	X
iPad Performance Testing	X		X	X		X		X	X	X
Blood Draw ($\Delta 9$ -THC levels)	X		X	X	X	X		X	X	X

Driving simulations: Simulation hardware will consist of a 3-screen, wide field-of-view monitor setup, steering wheel, and accelerator and brake pedals. The fully interactive simulations will assess lane tracking (standard deviation of lateral position [SDLP], or “weaving”), response to divided attention stimuli (accuracy, response time), car following, and performance during scenarios simulating routine driving as well as crash avoidance situations.

Participants in the simulator study will also be assessed for far visual acuity (Snellen Visual Acuity eye chart; need to have acuity of 20/40 or better, with or without correction), color vision, and contrast sensitivity (Vistech Contrast Sensitivity (Pelli-Robson Chart)). Participants will complete an orientation and practice drive prior to the initial simulation, in order to familiarize them with the controls and roadways.

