18. RISK/BENEFIT RATIO

There is a substantial disconnect between the therapeutic use of cannabis and research on the risks and benefits of this practice. Although edible marijuana merchandise has become widely available at medical dispensaries, there is little information in the literature on the medical efficacy of these products ⁶². Pharmacologic oral preparations, which like the edible products, avoid deleterious effects upon the respiratory system, have had more attention from the scientific community ⁶³⁻⁶⁹. However, some experts have opined that whole plant cannabis is superior to the FDA approved oral cannabinoid preparations, e.g., synthetic tetrahydrocannabinol (dronabinol, Marinol®) and/or the synthetic analog of Δ9-THC (nabilone, Cesamet®). As testament to this belief, oral cannabinoids have been on the market in the United States for many years and are not widely used ⁷⁰. Peak plasma concentrations occur 1 to 6 hours after ingestion, with a magnitude approximately 10% of that achieved with smoking ⁷¹. As a result of the pharmacokinetics of oral preparations, it has been postulated that the preference expressed by patients for herbal cannabis is a result of the faster onset and shorter duration of action allowing titration of dose to the desired effect ⁷². The present study will compare the risk benefit ratio of herbal cannabis to an oral preparation (dronabinol). We know that cannabinoids appear to have some benefit in alleviating a heterogeneous collection of neuropathic pain conditions ^{2, 3}. Preliminary recommendations have been issued from the College of Family Physicians in Canada to help guide clinicians in prescribing cannabis for the treatment of for chronic noncancer pain ⁷³. But we do not know if chronic low back pain will respond to cannabis (or dronabinol).

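### The 3-4 h no-driving instruction and the roughly 4 h of clean first-dose observation both end before the upper end of the protocol's own 1-6 h range for oral peak concentration, and the plan does not reconcile them

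*Protocol*

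**What the plan says.** **At home.** The risk-mitigation list in Protocol section 15 reads "We will instruct subjects not to drive a car or operate heavy machinery for 3-4 hours after use of medicinal cannabis", then "or longer if larger doses are used or the effects of impairment persist". The next sentence adds: "They will use a designated driver for automobile transportation if they have to go out sooner than 3-4 hours after taking this medicine". Section 5 describes the active treatments together as "two types of medicinal cannabis for eight weeks", which suggests that the term covers dronabinol. Under section 9 every participant takes both a vaporized and an oral product, and SAP section 1 assigns 40 of 120 to active dronabinol.

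On timing, section 18 says of oral preparations that "Peak plasma concentrations occur 1 to 6 hours after ingestion", at about a tenth of the level reached by smoking. Section 7 reports a laboratory comparison in which peak changes in pain sensitivity and tolerance were similar for the two products, "although dronabinol produced analgesia that was of a longer duration".

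**On the driving day.** In section 9 and its Table 3, both products are taken between Hours 1 and 2 and again between Hours 5 and 6. "By conducting repeat assessments for four hours following the first vaporization", the text says, "we will be able to determine at what point participants no longer exhibit acute effects for each of the study medications". The three hours after the second dose are meant to show whether effects are similar or cumulative. The simulator runs at Hours 1, 2, 3, 5, 6, 7 and 8, and blood THC is drawn every hour.

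SAP 4.2.4 tests recovery to the Hour 1 baseline and does not say which hours enter that test. SAP 4.2.3 defines a psychoactive-effects AUC over 1 to 6 hours after the first dose. SAP 4.3.2 acknowledges a delayed effect of dronabinol, but only for an analysis of pain reduction.

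**The concern.** There are two separate issues, linked by one figure in section 18.

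The first is participant safety. A participant who follows the stated interval exactly may be outside it while oral THC is still rising. The extension depends on larger doses, which are not defined, or on impairment that persists. Neither condition describes a peak that is yet to come.

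The second is what Aim 3 can conclude. Suppose a dronabinol participant's concentration peaks late. That participant may be near the Hour 1 level throughout the clean window and be read as unaffected or recovered. This could make dronabinol's effect on driving look smaller or shorter than it is relative to vaporized cannabis.

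**Working it through.** No power or alpha figure enters this point. The check is timeline arithmetic.

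**Inputs**
- No-driving interval: 3-4 h (Protocol 15)
- Oral peak plasma concentration: 1-6 h (Protocol 18)
- First dose between Hours 1 and 2, second between Hours 5 and 6 (Protocol 9, Table 3)
- Stated observation: 4 h after the first dose, 3 h after the second (Protocol 9)
- AUC window: 1-6 h after the first dose (SAP 4.2.3)

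**Step 1. Reproduce the stated windows.** Table 3 does not fix the dosing minute, so I take both extremes.

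| | Doses right after Hours 1 and 5 | Doses right before Hours 2 and 6 |
|---|---|---|
| Clean window after dose 1 | 5 - 1 = 4 h | 5 - 2 = 3 h |
| Window after dose 2 | 8 - 5 = 3 h | 8 - 6 = 2 h |
| Simulator, time since dose 1, before redosing | 1, 2, 4 h | 0, 1, 3 h |
| Hours 6-8, time since dose 1 | 5, 6, 7 h | 4, 5, 6 h |

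Early dosing reproduces the plan's 4 h and 3 h. Late dosing shortens each by an hour. With no simulator run at Hour 4, only three runs fall between the doses.

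**Step 2. Gap to the upper end of the oral range.**
- Instruction: 6 - 4 = 2 h to 6 - 3 = 3 h
- Clean first-dose window: 6 - 4 = 2 h (3 h with late dosing)
- Second-dose window: 6 - 3 = 3 h (4 h with late dosing)

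Each window overlaps the early part of the range. It is the upper part that is missed.

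**Step 3. How much of the range is missed.** By length, (6 - 3)/5 = 60% of the range lies beyond 3 h and (6 - 4)/5 = 40% lies beyond 4 h. The share of participants who peak there is not in the documents. Purely as assumptions:

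| Assumed distribution of peak time on 1-6 h | Beyond 3 h | Beyond 4 h |
|---|---|---|
| Uniform | 60% | 40% |
| Triangular, mode 1 h | 36% | 16% |
| Triangular, mode 2 h | 45% | 20% |
| Triangular, mode 3 h | 60% | 27% |
| Triangular, mode 4 h | 73% | 40% |

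For example, with mode 1 h the share beyond 3 h is (6 - 3)²/(5 × 5) = 9/25 = 36%. The spread shows how little can be said without data.

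**Step 4. What Hours 6-8 add.** They reach 5-7 h after the first dose (4-6 h with late dosing), so observation does extend to 6 h. By then both products have been given again, and the effect of the first oral dose cannot be separated from that of the second.

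**Step 5. The SAP 4.2.3 AUC.** With early dosing, 1-6 h after dose 1 means Hours 2-7, and Hours 6 and 7 follow the second dose. With late dosing it means Hours 3-8, and Hours 6, 7 and 8 follow it. So 2 or 3 of the 6 points described as following the first dose also follow the second.

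**The case against.** The strongest case on the other side has several parts.

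- **Concentration is not effect.** A reader might infer that participants can be outside the interval before peak effect. Section 18 times plasma concentration only and puts it at about a tenth of that from smoking. No text times oral impairment, and the longer duration in section 7 concerns analgesia. This stands. Section 7 also means that a low plasma level is not shown to imply a small or brief effect, so the mismatch remains.
- **The interval is a minimum.** One condition for extending it is dose, so it does not depend wholly on self-perceived impairment. This stands too, but neither condition covers a rising concentration.
- **Clearance to drive.** A reader might infer that the trial clears participants to drive. No such step is described, and section 20 has participants arrange their own transport.
- **Tablets left out.** A reader might infer that the instruction omits them. The synopsis points the other way. Consent pages and appendices were not available, so what participants are actually told cannot be judged.
- **Daily totals.** A reader might multiply by three daily doses and compare 3 × 6 = 18 h with 3 × 3 to 3 × 4 = 9-12 h. That assumes every dose peaks at 6 h, no doses overlap, and tablets and vaporization coincide. The documents give no clock times, and each use restarts the interval.
- **The second window.** Section 9 assigns it to cumulative effects, so it is not a failed recovery window. That is correct, and it is why it cannot rescue the recovery claim.
- **Standing of the analysis.** Driving is a secondary outcome in a substudy, so the primary pain comparison is untouched.

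**Conclusion.** The point holds in two limited parts.

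1. Section 15's fixed interval can end 2-3 h before the upper end of section 18's oral concentration range. The extension clause does not deal with a concentration still rising, and the documents do not reconcile the two sections. All 120 participants fall under the instruction, and about 40 take active dronabinol.
2. Clean first-dose observation ends at about 4 h, with simulator runs at about 1, 2 and 4 h. The design therefore cannot establish recovery from oral THC for participants who peak late, and section 9's statement about each medication goes further than the data can.

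The gaps rest only on the documents' own times, with dosing at either end of the slots in Table 3. The number of late peakers, and so the size of any bias in Aim 3, is unknown. The documents do not show that anyone would drive while impaired.

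**What to change.** 1. **Safety wording.** The investigators and IRB should reconcile Protocol section 15 with sections 7 and 18. The wording should spell out that the instruction covers the tablets as well as vaporization, as the synopsis implies. No interval is proposed here; that is a clinical decision.
2. **Recovery claim.** In Protocol section 9 and SAP 4.2.4, limit the conclusion, for the oral arm in particular, to no impairment detected up to about 4 h after the first dose. State that Hours 6-8 are analyzed as cumulative two-dose effects and do not enter the recovery test.
3. **Descriptive THC profile.** Report the hourly THC profile by arm, with the number of participants whose level was still rising at Hour 5, the last sample before redosing. Do not exclude or reclassify anyone on this basis. It is a post-randomization variable that differs by route, and a passed peak cannot be verified in the late peakers at issue.
4. **AUC.** Reconcile the 1-6 h window in SAP 4.2.3 with Table 3: either end it before the second dose or describe it as a two-dose measure.

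The cost is wording in the two documents and one descriptive table from blood samples already planned. The price is a narrower recovery claim for dronabinol.
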